3.1. General Objective

- 1) To determine the efficacy and safety of rESWT in combination with C-E drug therapy in treatment of chronic non-specific low back pain.

3.2. Specific Objectives

- 1) To determine the efficacy of combined rESWT /C-E drug therapy, rESWT alone and C-E drug therapy alone in treatment of chronic non-specific low back pain.
- 2) To evaluate patient's pain score, Oswestry Disability Index score, Clinical Global Impression score, and anxiety and depression score (including GAD-7, PHQ-9, PHQ-15 and pain disaster score) at baseline and at two weeks, four weeks, 12 weeks and 24 weeks after baseline.

- 3) To evaluate patient's lumbar curvature using lateral X-ray radiographs at baseline and at 12 weeks after baseline.
- 4) To evaluate patient's cross-sectional area of the paravertebrate muscles using MRI at baseline and at 12 weeks after baseline.
- 5) To evaluate safety of rESWT in treatment of chronic non-specific low back pain.

4. Study protocol

4.1. Introduction

An advanced study design of a clinical trial is ways more than just to decide how many patients will be treated with treatment X and how many patients with treatment Y, and how treatments X and Y should be performed. Actually an advanced study design of a RCT has to consider everything that will be checked later in assessments of the methodological quality of a RCT of health care interventions. There are at least six different assessments available:

1. Jadad et al. (1996) – This is a very basic assessment, attributing to each RCT a quality score out of a maximum of six points: (1) Was the generation of randomization sequence described? (2) Was the method of allocation concealment described? (3) Was an intention to treat analysis used? (4) What number of patients was lost to follow-up? (5) Was the outcome assessment blind? and (6) Was the patient blind to treatment allocation? The design of the proposed study on rESWT for chronic soft tissue wounds considers all these aspects.
2. The DELPHI list (Verhagen et al., 1998) – The DELPHI list consists of the following questions: (1) Was a method of randomization performed? (2) Was the treatment allocation concealed? (3) Were the groups similar at baseline regarding the most important prognostic indicators? (4) Were the eligibility criteria specified? (5) Was the outcome assessor blinded? (6) Was the care provider blinded? (7) Was the patient blinded? (8) Were point estimates and measures of variability presented for the primary outcome measures? (9) Did the analysis include an intention-to-treat analysis? The design of the proposed study on rESWT for chronic soft tissue wounds considers all these aspects, except of the fact that the care providers will not be blinded.
3. The PEDro scale (Blobaum, 2006) (outlined in detail in Section 1 above) - This scale is a development of the DELPHI list and consists of a total of 10 scale items, including random allocation, concealment of allocation, comparability of groups at baseline, blinding of patients, therapists and assessors, analysis by intention to treat and adequacy of follow-up,

between-group statistical comparisons, and reports of both point estimates and measures of variability. The design of the proposed study on rESWT for chronic non-specific low back pain considers all these aspects, except of the fact that patients and therapists will not be blinded (which is in principle not possible when comparing combined ESWT /C-E drug therapy with ESWT alone and C-E drug therapy alone).

[figure not shown]
4. Chalmers et al. (1981) – This assessment consists of two evaluation forms that include 29 individually scored items, allowing a maximum score of 100.
5. Downs and Black (1998) – This assessment includes 27 individually scored items, allowing a maximum score of 32.
6. The CONSORT statement (Schulz et al., 2010) – The CONSORT statement is intended to improve the reporting of RCTs, enabling readers to understand a trial's design, conduct, analysis and interpretation, and to assess the validity of its results.

The assessments of Chalmers et al. (1981), Downs and Black (1998) and Schulz et al. (2000) are very similar. However, Downs and Black (1998) provide the most specific questions. Accordingly, the design of the proposed study on rESWT for chronic non-specific low back pain was developed according to the criteria set out by Downs and Black (1998). The proposed study on rESWT for chronic non-specific low back pain will achieve a very high rating on the assessment by Downs and Black (1998).

4.2. Study design

- Randomized controlled trial (RCT), no blinding of patients and therapists applying the treatments (the rationale for this is provided in Section *Blinding of therapists and assessors* below, there will be blinding of evaluators/assessors).

4.3. Schematic diagram of study design:

4.4. Inclusion criteria

- Adults (both male and female) with non-specific low back pain for more than three months.
- Age range: between 18 and 80 years.
- Willingness of the patient to participate in the study, and written informed consent signed and personally dated by the patient.
- Chronic non-specific low back pain clinically diagnosed as repeated lumbar sourness and swelling pain or a chronic progressive process, accompanied by (i) X-ray examination to exclude lumbar vertebrate fractures, spondylolysis, spondylolisthesis and severe osteoporosis, and/or (ii) MRI with normal signal or low nucleus pulposus signal.
- No contraindications for rESWT.

4.5. Exclusion criteria

- Children and teenagers below the age of 18.

- Elderly aged >80 years old
- No willingness of the patient to participate in the study, and/or written informed consent not signed and not personally dated by the patient.
- Previous spinal fracture or spinal surgery.
- Protrusion of a lumbar intervertebral disk, ankylosing spondylitis, scoliosis, lumbar spondylolisthesis and lumbar spondylolysis.
- Systemic disorders and psychiatric disorders.
- Contraindications of C-E drug treatment, including:
 - treatment of patients allergy to celecoxib, eprisine or sulfonamides,
 - patients with gastrointestinal bleeding or bleeding history,
 - patients with renal dysfunction,
 - patients with severe heart failure, and
 - lactating women.
- Contraindications of rESWT:
 - treatment of pregnant patients,
 - treatment of patients with blood-clotting disorders (including local thrombosis),
 - treatment of patients treated with oral anticoagulations,
 - treatment of patients with local tumors,
 - treatment of patients with local bacterial and/or viral infections (including lumbar vertebral tuberculosis), and
 - treatment of patients treated with local corticosteroid applications in the time period of six weeks before the first rESWT session (if applicable).
- Participation in any other clinical trial in the time period of 12 weeks before potential inclusion in the proposed study.

4.6. Groups and treatments

Patients in the rESWT plus C-E drugs group will receive the below:

- Celecoxib (1 × 200 mg per day for moderate pain [NRS 4-6; c.f. Section 4.11.2 below] or 2 × 200 mg per day [NRS 7-10]) for four weeks.
- Eperisine (3 × 50 mg per day) for four weeks.
- Four rESWT sessions with the Swiss Dolorclast and the EvoBlue handpiece, as follows:
 - One rESWT session per week.

- 4 × 1000 rESWs per session (1000 rESWs each applied to the left and the right paravertebrate muscles above L3 to S1 using the 36-mm applicator, plus 1000 rESWs each applied to the left and the right sacroiliacal joint using the 15-mm convex applicator, in prone position of the patient).
- rESWs applied at 15 Hz
- Air pressure of the Swiss DolorClast (and, thus, the energy flux density of the applied rESWs) gradually increased during the first 200 rESWs each until the maximum dyscomfort the patient can tolerate will be reached, followed by 800 rESWs at this air pressure / energy flux density.
- No application of local anaesthetics (Rompe et al., 2005; Schmitz et al., 2013; 2015).

Patients in the rESWT group will receive the below:

- Four rESWT sessions with the Swiss Dolorclast and the EvoBlue handpiece as described above for the *rESWT plus C-E drugs* group.

Patients in the C-E drugs group will receive the below:

- Celecoxib and Eperisome as described above for the *rESWT plus C-E drugs* group.

In addition, all patients will be advised to perform simplified, safe core stability training and flexion relaxation training at home, which is mainly based on the contraction of the lumbar muscles, under the guidance of a unified rehabilitation training video (two training sessions per week; each training session lasting for approximately 20 minutes; training for 24 weeks).

4.7. Recruitment of patients

- Patients in the *rESWT plus C-E drugs* group, the *rESWT* group and the *C-E drugs* group will be selected from the same hospital (Department of Pain Medicine at the First Affiliated Hospital of Zhejiang University), and will be recruited over the same period of time.
- Recruitment of patients will start immediately after approval of the study by the Medical Research and Ethics Committee of the First Affiliated Hospital of Zhejiang University.
- Patients will be recruited during regular visits to the Department of Pain Medicine at the First Affiliated Hospital of Zhejiang University. All potential patients that fulfill the inclusion criteria and do not fulfill any of the exclusion criteria outlined above will be offered to participate in the proposed study until the total number of patients (*rESWT plus C-E drugs* group: n=50; *rESWT* group: n=50; *C-E drugs* group: n=50) will be recruited. Accordingly, the subjects that

will be prepared to participate in the proposed study will be representative of the entire population from which they were recruited. We will report the proportion of those asked who agreed.

- The intervention will be undertaken in a specialist centre that is representative of the hospitals in China most of the source population would attend if seeking treatment of chronic non-specific low back pain.

4.8. Informed Consent Process

Should patients agree to be part of the proposed study, they will be guided through the informed consent process first, as described here. The Informed Consent Process will be done at the Department of Pain Medicine at the First Affiliated Hospital of Zhejiang University. A copy of the Participant Information Sheet will be given to them. The patient will be given sufficient time to read and understand everything written on the document. The Principal Investigator will be there to explain and answer any queries that may arise. The patient will sign the Informed Consent Form if agreeable thereafter.

4.9. Randomization and blinding of patients

- Patients that fulfill the inclusion criteria and do not fulfill any of the exclusion criteria will be randomly allocated to either rESWT plus C-E drugs (n=50), rESWT alone (n=50) or C-E drugs alone (n=50), respectively (sample size is addressed in Section 5.1. *Power analysis* below).
- Randomization will be performed as described by Rompe et al. (2008) in a randomized, controlled study on rESWT for Achilles tendinopathy. Specifically, a computerized random-number generator will be used to formulate an allocation schedule. Subjects will be randomized to either treatment (rESWT plus C-E drugs, rESWT alone or C-E drugs alone), with use of the method of randomly permuted blocks. The randomization scheme will be generated with the use of the website www.randomization.com. One hundred and fifty patients will be randomized into five blocks. A medical assistant at the Department of Pain Medicine at the First Affiliated Hospital of Zhejiang University will allocate interventions by means of opaque sealed envelopes that will be marked according to the allocation schedule. The medical assistant will be unaware of the size of the blocks.
- The randomized intervention assignment as outlined above will be concealed from both patients and health care staff until recruitment will be complete and irrevocable.

- Neither patients nor therapists will be blinded in the proposed study. The therapist will be the person who will administer rEWST to the patient.
- The assessor will be blinded in the proposed study. The assessor is the person who will assess treatment success during follow up.

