4.10. Study treatment and visits

Study visits of patients in the *rESWT plus C-E drugs* group and the *rESWT* group will take place at 0, 1, 2 and 3 weeks for administering rESWT. A single study visit of patients in the *C-E drugs* group will take place at 0 weeks.

In addition,

- at two weeks (i.e., after two rESWT sessions and immediately before the third rESWT session in case of patients in the *rESWT plus C-E drugs* group and the *rESWT* group),
- four weeks (i.e., one week after the last rESWT session in case of patients in the *rESWT plus C-E drugs* group and the *rESWT* group)
- 12 weeks and
- 24 weeks after baseline

treatment outcome will be evaluated (separate visits at four weeks, 12 weeks and 24 weeks after baseline in case of patients in the *rESWT plus C-E drugs* group and the *rESWT* group, as well as separate visits at two weeks, four weeks, 12 weeks and 24 weeks after baseline in case of patients in the *rESWT* group).

The investigator will perform the following procedures at the first visit:

- check eligibility,
- obtain informed consent,
- perform randomization, and
- collect patient's demographics & medical history.

Furthermore, the investigator will perform the following procedures at all visits:

- record any concomitant medication,
- perform clinical examination,
- report adverse events (AE) and serious adverse events (SAE), and
- complete relevant section of case report form (CRF)

Study visits and procedures are summarized in Tables 5 and 6 below.

Table 5. Study visits and procedures planned for the *rESWT plus C-E drugs* group and the *rESWT* group

	Screening, baseline assessment, randomization and first treatment	Additional study visits and follow-up examinations				Additional follow-up examinations	End
Visit	1	2	3	4	5	6	7
Timeline	0	1 wk	2 wks	3 wks	4 wks	12 wks	24wks
Procedures							
Check eligibility	X						
Obtain informed consent	X						
Perform randomization	X						
Collect patient's demographics & medical history	X						
Record any concomitant medication	X	X	X	X	X	X	X
Perform clinical examination	X	X	X	X	X	X	X
Dispense rESWT	X	X	X	X			
Perform efficacy assessment					X	X	X
Report AE and SAE	X	X	X	X	X	X	X
Complete relevant section of CRF	X	X	X	X	X	X	X

Table 6. Study visits and procedures planned for the *C-E drugs* group

	Screening, baseline assessment, randomization and first treatment	Follow-up examinations			End
Visit	1	2	3	4	5
Timeline	0	2 wks	4 wks	12 wks	24wks
Procedures					
Check eligibility	X				

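### Section 4.9 relies on an undisclosed block size but prints figures that imply it, and 4.9 and 4.10 differ on who allocates: a modest, cheaply removed risk to concealment

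*Combined protocol and SAP*

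**What the plan says.** Section 4.9 of the combined protocol and SAP describes a computer-generated schedule made "with use of the method of randomly permuted blocks". Patients are "randomly allocated to either rESWT plus C-E drugs (n=50), rESWT alone (n=50) or C-E drugs alone (n=50), respectively". It then states: "One hundred and fifty patients will be randomized into five blocks". No stratification is described.

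Three safeguards follow in the same section:

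- A medical assistant in the recruiting department "will allocate interventions by means of opaque sealed envelopes that will be marked according to the allocation schedule".
- On knowledge of the block size, it says: "The medical assistant will be unaware of the size of the blocks".
- The assignment "will be concealed from both patients and health care staff until recruitment will be complete and irrevocable".

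The section also says: "Neither patients nor therapists will be blinded in the proposed study". Section 4.7 places all recruitment in one hospital department.

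Section 4.10 gives the investigator's tasks at the first visit. They include checking eligibility, obtaining consent and "perform randomization, and" collecting demographics and history. Tables 5 and 6 place randomization and first treatment at that same visit.

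**The concern.** Withholding the block size is meant to stop staff from working out the next assignment from earlier ones. That fails for anyone who can derive the size, and the protocol prints the total, the number of blocks and the arm sizes side by side.

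The setting makes a tally practical. There is one department and one unstratified sequence, treatment is open-label, and it starts at visit 1. Opaque envelopes hide the next card but not what the opened cards imply about it. The concealment sentence cannot mean that past assignments stay hidden until the whole trial has recruited, because patients and therapists are not blinded. Read patient by patient, it does not prevent counting.

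At stake is selective or timed enrolment by someone who can foresee an assignment. The primary outcome is a patient-reported questionnaire score (Section 4.11.1), and treatment success is compared with an unadjusted Fisher's exact test (Section 5). Adjustment could not reliably repair selection on unmeasured factors in any case.

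The separation of enrolment from allocation in 4.9 also matters less if, as 4.10 reads, the person who enrols also randomizes.

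**Working it through.** **Inputs (Section 4.9):** 150 patients, 5 permuted blocks, 3 arms, 50 per arm. **Assumptions:** equal blocks, and all earlier allocations visible.

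**1. Implied block size.** 150 / 5 = 30 per block, and 30 / 3 = 10 per arm per block. Check: 5 × 10 = 50 per arm, as stated.

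**2. Allocations certain in advance.** An allocation is certain when every place left in the block, itself included, belongs to one arm. The chance that the last j places all belong to one arm is

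3 × [10 × 9 × … × (11 − j)] / [30 × 29 × … × (31 − j)].

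| Place in block | j | Chance that it is certain |
|---|---|---|
| 30 | 1 | 1.000 |
| 29 | 2 | 270/870 = 0.310 |
| 28 | 3 | 2,160/24,360 = 0.089 |
| 27 | 4 | 15,120/657,720 = 0.023 |
| 26 | 5 | 90,720/17,100,720 = 0.005 |

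Summed over j = 1 to 10, this equals 3 × 10 / (30 − 10 + 1) = 30/21 = 1.43 per block. Over five blocks it is 5 × 1.43 = 7.1 of 150, or 4.8%.

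The last block's 1.43 would be known anyway from the printed 50 per arm. The number of blocks itself therefore adds about 4 × 1.43 = 5.7.

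**3. Allocations with at least one arm ruled out.** For a given arm, the expected number of places after it is used up is 20/(30 − 20 + 1) = 20/11 = 1.82. Over three arms, less the places where two arms are used up, this is 3 × 1.82 − 1.43 = 4.03 per block. Over five blocks it is 20.1 of 150, or 13.4%.

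**4. Best guess.** Always naming the arm with most places left in a known block of 30 is right for 68.5 of 150 allocations (45.7%), against 50 of 150 (33.3%) by chance. But the arm with most places left is also the arm used least so far, because every completed block is balanced. Naming the least-used arm needs only a running tally. Simulated for five blocks of 30 without knowledge of the size, it gives the same 45.7%. This rate comes from permuted blocks with visible allocations, not from printing the number of blocks.

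**5. Effect of other block sizes.** The same least-used-arm guess was simulated with the sizes hidden, drawn at random and the list cut at 150. The sizes are assumptions.

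| Block sizes | Best guess correct |
|---|---|
| 30 (as implied) | 45.7% |
| 24 to 36, in steps of 3 | 45.1% |
| 9, 12, 15 | 50.8% |
| 6, 9, 12 | 52.7% |

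Small varying blocks make guessing easier, and large varying blocks do not. With sizes of 24 to 36, cutting the list at 150 left the largest and smallest arms about 2 patients apart on average. A small fixed size that became known would be worse still: size 6 gives 30 of 150 (20%) certain and 56.1% guessed correctly.

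**6. Who allocates.** In 4.9 the medical assistant allocates by envelope. In 4.10 the investigator's first-visit list covers eligibility, consent and randomization. The two descriptions name different people for the same step.

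**The case against.** - **The block size is inferred.** Section 4.9 gives the number of blocks, not their size, and does not say they are equal. This stands as a stated assumption. The text refers to one size, the 10/10/10 split is exact, and nothing says that sizes vary. If they do vary, knowing there are five blocks reveals little beyond what 50 per arm already does.
- **There is no strict contradiction.** The statement about block size concerns the medical assistant, and nothing says the assistant receives the protocol. This stands. The exposure lies more with the enrolling investigator, who can be assumed to have the protocol and about whom 4.9 makes no such statement.
- **The effect is small and late.** About 143 of 150 allocations stay uncertain, and certainty before place 26 of a block is very rare. This stands and limits the weight of the point.
- **Other safeguards exist.** Section 4.7 requires all eligible patients to be offered participation and the agreement rate to be reported. Section 4.9 specifies opaque sealed envelopes. Section 5 compares age, gender, body mass index, occupation and pain duration between groups. These could expose gross selection, but they do not stop counting.
- **The 4.10 entry may be only a schedule item,** meaning that the assistant opens the envelope during visit 1. That reading is possible. It calls for clarification and does not show that the enroller opens envelopes.

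A reader might infer that concealment is lost, or that disclosure raises correct guessing from 33.3% to 45.7%. The documents support neither. Nothing shows that staff would tally or act on a tally, and the 45.7% arises without knowledge of the block size.

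**Conclusion.** The point holds in a limited form. Section 4.9 relies on an undisclosed block size while printing figures that imply it. With equal blocks, visible allocations and someone at the site who keeps count, about 7.1 of 150 allocations (4.8%) are certain in advance, and 5.7 of these are attributable to the printed number of blocks. If the sizes in fact vary, only about 1.4, at the end of the last block, would be certain. Separately, 4.9 and 4.10 need to be reconciled on who allocates. This is a modest risk to concealment, worth removing because prevention is cheap and later correction is unreliable.

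**What to change.** 1. Remove the number of blocks from the site-facing protocol. Put block details in a restricted document held by someone not involved in enrolment. Section 5 names the external statistics institute only for choosing a missing-data method, so using it here would be a new task to agree.
2. For patients not yet randomized, regenerate the list with undisclosed sizes that vary but stay large, for example around 24 to 36. Small varying blocks should be avoided because they raise predictability.
3. Reconcile 4.10 and Tables 5 and 6 with 4.9. The investigator should request the next sequentially numbered envelope from the medical assistant only after eligibility, consent and baseline data are recorded.

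The cost is a regenerated list, a custodian outside enrolment, and possibly a slight final imbalance between arms if recruitment stops within a block. The total sample size, visits and treatments do not change.

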4.10. Study treatment and visits

Study visits of patients in the *rESWT plus C-E drugs* group and the *rESWT* group will take place at 0, 1, 2 and 3 weeks for administering rESWT. A single study visit of patients in the *C-E drugs* group will take place at 0 weeks.

In addition,

- at two weeks (i.e., after two rESWT sessions and immediately before the third rESWT session in case of patients in the *rESWT plus C-E drugs* group and the *rESWT* group),
- four weeks (i.e., one week after the last rESWT session in case of patients in the *rESWT plus C-E drugs* group and the *rESWT* group)
- 12 weeks and
- 24 weeks after baseline

treatment outcome will be evaluated (separate visits at four weeks, 12 weeks and 24 weeks after baseline in case of patients in the *rESWT plus C-E drugs* group and the *rESWT* group, as well as separate visits at two weeks, four weeks, 12 weeks and 24 weeks after baseline in case of patients in the *rESWT* group).

The investigator will perform the following procedures at the first visit:

- check eligibility,
- obtain informed consent,
- perform randomization, and
- collect patient's demographics & medical history.

Furthermore, the investigator will perform the following procedures at all visits:

- record any concomitant medication,
- perform clinical examination,
- report adverse events (AE) and serious adverse events (SAE), and
- complete relevant section of case report form (CRF)

Study visits and procedures are summarized in Tables 5 and 6 below.

Table 5. Study visits and procedures planned for the *rESWT plus C-E drugs* group and the *rESWT* group

	Screening, baseline assessment, randomization and first treatment	Additional study visits and follow-up examinations				Additional follow-up examinations	End
Visit	1	2	3	4	5	6	7
Timeline	0	1 wk	2 wks	3 wks	4 wks	12 wks	24wks
Procedures							
Check eligibility	X						
Obtain informed consent	X						
Perform randomization	X						
Collect patient's demographics & medical history	X						
Record any concomitant medication	X	X	X	X	X	X	X
Perform clinical examination	X	X	X	X	X	X	X
Dispense rESWT	X	X	X	X			
Perform efficacy assessment					X	X	X
Report AE and SAE	X	X	X	X	X	X	X
Complete relevant section of CRF	X	X	X	X	X	X	X

Table 6. Study visits and procedures planned for the *C-E drugs* group

	Screening, baseline assessment, randomization and first treatment	Follow-up examinations			End
Visit	1	2	3	4	5
Timeline	0	2 wks	4 wks	12 wks	24wks
Procedures					
Check eligibility	X				
Obtain informed consent	X				
Perform randomization	X				
Collect patient's demographics & medical history	X				
Record any concomitant medication	X	X	X	X	X
Perform clinical examination	X	X	X	X	X
Perform efficacy assessment		X	X	X	X
Report AE and SAE	X	X	X	X	X
Complete relevant section of CRF	X	X	X	X	X

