4.12. Blinding of therapists and assessors

- Therapists applying the treatments will not be blinded. This will be done because even when using coded “active” and “placebo” handpieces in a study on ESWT, blinding of ESWT therapists can only be achieved when another person prepares the device before rESWT or sham treatment. This, however, is almost impracticable and has not been done in any of the more than 100 studies on rESWT and fESWT listed in the PEDro database (Schmitz et al., 2015). The solution to this issue is a strict, standardized way of interaction between the ESWT therapist and the patients, irrespective of treatment allocation (as mentioned in a study by Buchbinder et al., 2002). This approach will also be applied in the proposed study.
- All assessments before the first treatment (baseline) and during the follow-up period will be performed by assessors blind to the intervention.

5. Follow-up and statistical analysis

- Follow-up will be the same for all study patients.
- The design of the proposed study guarantees that there will be full compliance with the allocated treatment and, thus, no contamination of one group.
- The patient's age, gender, body mass index, job occupation and duration of non-specific low back pain are potential confounding factors when treating chronic non-specific low back pain with rESWT. Normal distribution of these data will be tested using the D'Agostino-Pearson omnibus test. In case of passing the normality test we will report mean and standard error of the mean of these variables; otherwise we will report inter-quartile ranges of these variables. Comparison between groups will be performed with ANOVA followed by Bonferroni post tests for pairwise comparisons in case of passing the normality test, or the nonparametric Kruskal-Wallis test followed by Dunns tests for pairwise comparisons in case of not passing the initial normality test.
- As outlined in Section "Primary clinical outcome and definition of treatment success" above, the primary clinical outcome will be the PSEQ score at 12 weeks after baseline. Treatment success (i.e., number of patients with individual improvement of PSEQ score by more than 20% at 12 weeks after baseline) will be tested with Fisher's exact test.

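### During treatment, adverse events are scheduled to be sought twice as often in both rESWT arms (weeks 1, 2, 3, 4) as in the C-E drugs arm (weeks 2, 4), so comparing non-serious AE counts with the C-E arm risks detection bias against rESWT

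*Combined protocol and SAP*

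**What the plan says.** Section 4.10 gives the two kinds of arm different visit schedules. In the combination arm and the rESWT-alone arm, visits of each "group will take place at 0, 1, 2 and 3 weeks for administering rESWT". For the drug arm: "A single study visit of patients in the *C-E drugs* group will take place at 0 weeks", followed by outcome visits.

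The same section says that "the investigator will perform the following procedures at all visits", and the list includes "report adverse events (AE) and serious adverse events (SAE), and" as well as clinical examination and concomitant medication. In Table 5 (both rESWT arms) the row "Report AE and SAE" is marked at weeks 0, 1, 2, 3, 4, 12 and 24. In Table 6 (C-E drugs arm) it is marked at weeks 0, 2, 4, 12 and 24. Clinical examination follows the same pattern.

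Section 3.2 lists as an objective: "To evaluate safety of rESWT in treatment of chronic non-specific low back pain". Section 10.2 accepts AEs that are volunteered, elicited by questioning or found on examination, and Section 10.1 has doubtful events counted as AEs. Section 5 states: "Follow-up will be the same for all study patients". It specifies no analysis of AEs.

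**The concern.** The C-E drugs arm is the only arm without rESWT, so it is the natural reference for what rESWT adds in harms. Two of the three detection routes in Section 10.2, questioning and examination, are scheduled twice as often in the rESWT arms while treatment is being given. Unequal looking can produce unequal counts even when true rates are equal.

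The exposed events are mild, short-lived and possible in any arm. The clearest case is the combination arm against C-E drugs alone. Section 4.6 gives both the same drugs for four weeks, and Section 6.1 lists exhaustion and dizziness among the drug effects. Those effects are sought weekly in one arm and fortnightly in the other. An apparent excess in the combination arm could be taken for a harm of rESWT, or for an interaction, when part or all of it came from the visit schedule.

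**Working it through.** The plan gives no AE rate, AE test or safety sample size, so it has no figure to reproduce. The visit counts come from the documents. Everything after step 1 is illustration on stated assumptions.

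**1. Scheduled AE enquiries (Tables 5 and 6)**

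| Period | Each rESWT arm | C-E drugs arm | Ratio |
|---|---|---|---|
| Weeks 1 to 4 | 4 (weeks 1, 2, 3, 4) | 2 (weeks 2, 4) | 2.0 |
| After week 4 | 2 (weeks 12, 24) | 2 (weeks 12, 24) | 1.0 |
| All post-baseline | 6 | 4 | 1.5 |
| Including week 0 | 7 | 5 | 1.4 |

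The imbalance lies wholly in the four treatment weeks.

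**2. Fixed look-back.** Assume that each enquiry captures only events from the last *r* days and that events fall evenly over 28 days. With *v* evenly spaced visits, the share captured is min(1, *v* × *r* / 28).

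- *r* = 7: 4 × 7/28 = 1.00 against 2 × 7/28 = 0.50; ratio 2.0. Shorter look-backs give the same ratio.
- *r* = 10: 1.00 (capped) against 2 × 10/28 = 0.714; ratio 1.4.
- *r* = 14: 1.00 (capped) against 2 × 14/28 = 1.00; ratio 1.0, so no bias.

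**3. Gradual forgetting.** Assume that the chance of reporting halves every *h* days. The average share recorded over a gap of *L* days is (1 − 2^(−L/h)) / ((L/h) ln 2), with *L* = 7 in the rESWT arms and *L* = 14 in the C-E arm.

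- *h* = 7: 0.721 against 0.541; ratio 1.33.
- *h* = 14: 0.845 against 0.721; ratio 1.17.
- *h* = 28: 0.918 against 0.845; ratio 1.09.

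**4. What this could do to a test.** Suppose someone compared the proportions with an AE using 50 patients per arm (Section 4.9) at two-sided 0.05, with the true four-week risk equal in both arms. With recorded risks p1 and p2 from step 2 and their mean p̄, the chance of a nominally significant excess in an rESWT arm is Φ[(p1 − p2 − 1.96 √(2p̄(1 − p̄)/50)) / √((p1(1 − p1) + p2(1 − p2))/50)].

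- *r* = 7: 15.5% at a true risk of 10% (recorded 10% against 5%), rising to 59% at a true risk of 40% (recorded 40% against 20%).
- *r* = 10: 7.3% to 22.3% over the same range.
- *r* = 14: the nominal 2.5%.

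The true risks of 10% to 40% are assumed. This is a normal approximation and is rough at the lowest counts.

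**The case against.** Several points on the other side stand.

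- **No between-arm AE test is planned.** Section 5 names none, and the safety objective could be met descriptively. The risk therefore attaches to any comparison of counts that is later made. The plan also has no rule against a naive comparison.
- **Volunteered events.** Section 10.2 does not limit recording to events present at a visit, and start and end dates are taken. Good recall over 14 days would remove the difference, so zero bias belongs in the range.
- **Direction and scope.** Any bias runs against rESWT, so it cannot make rESWT look falsely safe. Serious events are unlikely to be missed, and the two rESWT arms share one schedule.
- **Open label.** Patients and therapists know the allocation (Section 4.9), so equal enquiry alone would not make AE reporting fully comparable.
- **Attendance.** The weekly sessions require weekly visits. They do not require the between-arm comparison to rest on unequal enquiry.

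Some stronger readings are tempting but not supported. A reader might infer that the Section 5 sentence on equal follow-up is untrue. However, Section 4.11 defines the follow-up examinations as weeks 2, 4, 12 and 24 without distinction of arm, and weeks 1 and 3 are treatment visits, so the sentence can be read consistently with that definition. (Table 5 shows no efficacy assessment at week 2, unlike the text and Table 6; that is a separate point to reconcile.) A reader might also take bruising and numbness, which normally pass in one or two days, as the main example. Sections 6.1 and 10.6 list them as effects of rESWT at the treatment site. They have no counterpart in the C-E arm, so unequal enquiry cannot create a spurious difference in them.

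**Conclusion.** The unequal schedule is certain: 4 against 2 enquiries in the treatment period and 6 against 4 post-baseline, with nothing elsewhere in the protocol to offset it. The consequence is a risk of detection bias against rESWT in non-serious AE counts compared with the C-E arm. It would be too strong to say that a planned safety comparison is biased: no such comparison is specified, and the size cannot be fixed from the documents. On the assumptions shown, the ratio of recorded events with no true difference runs from 1.0 (complete 14-day recall) to about 2.0 (only the last 7 days recalled). No scenario favours the rESWT arms. This is a modest point about data collection and reporting. It is worth settling before data collection because enquiries not made at the time cannot be recovered.

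**What to change.** **Preferred.** Ask all three arms the same scripted AE question at weeks 2, 4, 12 and 24, each covering the time since the previous common visit. In the rESWT arms, put this question at weeks 2 and 4 whatever was recorded at weeks 1 and 3. State in Section 5 that between-arm AE comparisons use these enquiries plus all serious events, and that events recorded only at weeks 1 and 3 are listed separately. The enquiries then stand at 4 against 4. This needs no extra contacts; the cost is that some events seen at weeks 1 and 3 leave the between-arm comparison.

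**Alternative.** Add scripted AE telephone enquiries at weeks 1 and 3 to Table 6 for the C-E arm. This is about 50 × 2 = 100 short calls and gives 4 against 4 in weeks 1 to 4 and 6 against 6 post-baseline. It equalises questioning but not clinical examination, and adds a little contact in that arm. It would be a new provision, because Section 7.2 allows telephone contact only for patients who have withdrawn or been withdrawn.

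**In either case,** clarify in Section 5 that the sentence on equal follow-up refers to the follow-up examinations at weeks 2, 4, 12 and 24.
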